Comparison of Ideal vs. Actual Weight Base Factor Dosing

Version 2.0

October 12, 2016

Comparison of Ideal vs. Actual Weight Base Factor Dosing

Background

Hemophilia is an x-linked (mainly affecting males) genetic disorder characterized by a mutation in the clotting factor VIII gene (hemophilia A) or the clotting factor IX gene (hemophilia B) resulting in spontaneous and trauma-induced bleeding. This bleeding can be treated and prevented with clotting factor concentrate which has been available since the 1960s. A randomized clinical trial published in 2007 [Manco-Johnson, NJEM 2007] established that prophylactic treatment with factor several times a week prevents bleeding and adverse clinical outcomes due to bleeding such as joint arthropathy. Thus, prophylactic treatment with clotting factor became standard of care.

Clotting factor replacement is given intravenously and is based on a patient's weight. The clotting factor circulates in the plasma with a half-life of hours to days (depending on the product). It does not get distributed in the adipose (fat) tissue. Although total plasma volume might increase with body mass index, it does not increase proportionally. The current standard of calculating a patient's dose on actual body weight may overestimate the appropriate dose, and calculations based on ideal body weight may be more accurate. Inappropriate dosing may not only be harmful for the patient but also leads to unnecessary health care cost.

Hypothesis: Factor dosing based on ideal body weight will result in hemostatic factor levels (recovery of at least 66% of predicted).

Null Hypothesis: Factor dosing based on ideal body weight will not result in hemostatic factor levels (recovery of at least 66% of predicted).

Trial Design

This is a randomized, prospective, multicenter, open-label, cross-over study comparing the pharmacokinetics (PK) of ideal vs. actual body weight dosing of factor concentrate in overweight and obese participants with hemophilia A.

The study will be conducted at the Washington Center for Bleeding Disorders (WCBD), Oregon Health & Science University (OHSU), Seattle Children's Hospital (SCH) and Providence Sacred Heart Children's Hospital (SH). Ethics approval will be obtained at each individual location before trial enrollment begins for that location.

Primary outcomes:

1. To compare the recovery to a 50 units/kg ($\pm 20\%$) dose of factor VIII (FVIII) concentrate in participants age 12 and above with hemophilia A when calculated on *actual body weight (ABW)* versus *ideal body weight (IBW)*.
2. To determine the likelihood of under dosing when using IBW or over-dosing with ABW

Secondary outcomes:

[figure not shown]
- To determine the effect on half-life of these dosing strategies
- To determine the effect on PK differences of hemophilia severity
- To determine differences in participants receiving half-life (HL) vs. extended half-life (EHL) products
- To determine the differences, if any, between overweight and obese participants

Inclusion Criteria

- At least 12 years of age
- Hemophilia A
- Male gender
- Able and willing to comply with PK testing schedule
- Either overweight or obese BMI (using CDC definitions by age)

Table 1: The standard weight status categories associated with BMI ranges for adults (≥ 20 year old)

BMI	Weight Status
Below 18.5	Underweight
18.5 – 24.9	Normal or Healthy Weight
25.0 – 29.9	Overweight
30.0 and Above	Obese

Figure 1: The standard weight status categories associated with BMI ranges for boys (2 to 19 years)

Exclusion Criteria

- Inhibitor of > 0.6 BU twice in the past, or documented abnormal recovery of less than 66% (of expected) in the past.
- Known other bleeding disorder
- Known other prolongation in aPTT (lupus anticoagulant, FXII deficiency)
- Female gender

Recruitment

Participants will be recruited through the participating centers. Washington Center for Bleeding Disorders (WCBD), Oregon Health & Science University (OHSU), Seattle Children's Hospital (SCH) and Providence Sacred Heart Children's Hospital (SH). Cumulatively, up to 20 patients will be enrolled at all 4 sites.

Randomization

Randomization will be performed centrally at the Washington Center for Bleeding Disorders. When a participant has completed the consent and eligibility forms and is able to be enrolled, the participating center will contact WCBD to receive the subject ID and treatment arm assignment. Randomization will be determined by

blocked randomization. Subjects will be randomized to either undergo PK measurements based on actual body weight followed by ideal body weight OR PK measurements based on ideal body weight followed by actual body weight.

Study design - Primary outcome:

Participants age 12 and up and considered to be overweight or obese by either calculated BMI (ages 20 and over) or the McLaren method (ages 12 to 19) and diagnosed with hemophilia A of any severity will be enrolled.

There must be a period of at least 48 hours for standard half-life products or at least 72 hours for extended half-life products since the last dose of factor. Participants will be randomized to receive 50 U/kg ($\pm 20\%$) of the factor product they routinely use either based on IBW or ABW and will have pharmacokinetic (PK) labs drawn as described in the PK protocol section. After a period of at least 48 hours for standard half-life products or at least 72 hours for extended half-life products but no more than 60 days, participant will receive a second dose of factor at 50 U/kg ($\pm 20\%$) based on the alternate dosing strategy and will have a second set of PK labs drawn.

Patients may bring and infuse their own factor, have it infused by their parents or by the clinic staff. Should there be bleeding during the study, the bleed should be treated as per the patient's usual protocol.

PK studies will be delayed until the resolution of any acute bleeding episodes [after a period of at least 48 hours for standard half-life products or at least 72 hours for extended half-life products]. If the participant has an acute bleed after the recovery draw, then that episode will not be used in the analysis. The episode will be attempted again at a later date within the 2-month window.

Intention to treat:

If a participant experiences a 10% or greater change in BMI between the first and second dose, the participant will be included in the analysis.

Minimum of 8 participants ages 12 and over

Ideal body weight and BMI calculations:

BMI Calculations:

Sites shall use CDC website to calculate BMI for all participants and to determine if participants are overweight or obese.

Ages 12 to <20: <https://nccd.cdc.gov/dnpabmi/Calculator.aspx>

[figure not shown]
Ages 20 and older:

http://www.cdc.gov/healthyweight/assessing/bmi/adult_bmi/metric_bmi_calculator/bmi_calculator.html

IBW Calculations:

Ages 12 to <20: Sites shall use the McLaren method to calculate ideal body weight in participants under 20 years old. [Phillips et al 2007]

<http://www.cdc.gov/growthcharts/data/set1clinical/cj41c021.pdf>

Ages 20 and older: Sites shall use the following equation to calculate IBW in participants 20 years and older: $IBW = 50 \text{ kg} + (2.3 \text{ kg} * \text{every inch over 5 feet})$

PK Protocol:

PK studies will be measured in response to one 50 U/kg ($\pm 20\%$) dose of the participant's current product. Every effort shall be made to ensure the same size

vials and same lot numbers are used with the second dose to ensure the second dose is as similar to the first dose as possible. All participants will undergo PK testing twice: One test will be with 50 U/kg ($\pm 20\%$) for hemophilia A based on ideal body weight and the other test will be with 50 U/kg ($\pm 20\%$) for hemophilia A based on actual body weight.

Post dose blood draws cannot be pulled from the port/IV that was used to administer factor. Sites may infuse factor through a peripheral line and obtain post blood draws through a port.

Blood Draw Policy and Schedules: The baseline and the recovery draws for the first and second doses must be completed by the same laboratory (baseline laboratory). Baseline and peak (recovery) levels will be drawn in duplicate. The Duplicate draw will be spun and frozen for batch shipping/testing at the designated “reference” lab. Duplicate samples from OHSU and Seattle Children’s will be tested at WCBD, Duplicate samples from WCBD and Scared Heart will be tested at OHSU.

Blood draws to measure half-life are encouraged to be drawn in the baseline laboratory, but may be drawn in other local laboratories and shipped to the baseline laboratory for analysis. If the 30-minute recovery draw is missed participant can still be included with another attempt of the dose/PK draw if the second dose/draw falls within the 2 month window.

Hemophilia A – regular half-life product

Baseline – 30 \pm 10 minutes – 5 to 7 hours – 20 to 26 hours – 44 to 50 hours

Hemophilia A – extended half-life factor

Baseline – 30 \pm 10 minutes – 5 to 7 hours – 20 to 26 hours – 44 to 50 hours – 69 to 75 hours – 93 to 99 hours

Statistics:

The first primary endpoint will be assessed by evaluation of the mean paired difference in recovery between the two methods (IBW vs. ABW dosing) by paired t-test or by Wilcoxon signed-rank test if recoveries are skewed.

The second primary endpoint will be evaluated by extension of estimated recovery distribution to estimate the likelihood of failure (under-dosing or over-dosing) of each dosing strategy.

For the first of the above evaluation measures, assuming approximate normality of recoveries, we estimate having 80% power to detect a mean reduction of 1 standard deviation in a study of 16 subjects assuming an intra-class correlation of at least 0.2. Greater (lesser) intra-class correlation would increase (decrease) statistical power for this evaluation.

In the event that the study is underpowered (due to a lower than anticipated intra-class correlation), distributional summaries for each approach and for paired differences (including histograms) as well as for the intra-class correlation would be useful for design of future studies if the ideal weight base factor dosing is not deemed unacceptable

Collecting and Reporting Adverse Events:

Serious adverse events are defined as when the patient outcome is either death, life-threatening, hospitalization (initial or prolonged), disability or permanent damage, congenital anomaly/birth defect, required intervention to prevent permanent impairment or damage, or other serious, important medical events. Serious adverse events should be tracked per patient and reported centrally to the [Washington Center for Bleeding Disorders](#). Adverse events that do not meet the criteria for serious adverse events but qualify as Grade 3 or 4 adverse events will be recorded and reported.

Information to collect and report on adverse events includes patient details, suspected medicinal product, other treatments, details of suspected adverse reactions, details on the reporter of the event.

Funding: This research is funded by the Healthcare Authorities of Washington

References

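### The stated hypothesis sets ideal-weight recovery against 66% of predicted, but the only named test and the only power statement concern the paired difference between ideal- and actual-weight dosing

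*Protocol*

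**What the plan says.** - **Hypothesis (Protocol, Background).** The hypothesis is that IBW dosing reaches the 66% level. Its null reads: "Null Hypothesis: Factor dosing based on ideal body weight will not result in hemostatic factor levels (recovery of at least 66% of predicted"). Only one strategy is involved, and the comparator is a number.
- **Primary outcomes.** The first compares recovery after the two doses. The second is "To determine the likelihood of under dosing when using IBW or over-dosing with ABW".
- **Test (Statistics).** The first primary endpoint is assessed by "evaluation of the mean paired difference in recovery between the two methods (IBW vs. ABW dosing) by paired t-test", or by the Wilcoxon signed-rank test if recoveries are skewed. The second is evaluated by "extension of estimated recovery distribution to estimate the likelihood of failure (under-dosing or over-dosing) of each dosing strategy".
- **Power (Statistics).** The protocol gives 80% power for a mean reduction of 1 SD with 16 subjects and an intra-class correlation (ICC) of at least 0.2. It says that this concerns the first of the two evaluation measures. It states no alpha and no sidedness.
- **The 66% figure elsewhere.** Outside the hypothesis and null it appears only in Exclusion Criteria: "documented abnormal recovery of less than 66% (of expected) in the past". It does not appear in Statistics.
- **Numbers enrolled.** Recruitment says "up to 20 patients will be enrolled at all 4 sites". The study design section sets a minimum of 8 participants aged 12 and over.

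**The concern.** The hypothesis asks whether IBW dosing is adequate. The named test asks whether the two strategies differ. These are separate questions, and the answer to one does not give the answer to the other.

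The Background itself explains why: "Although total plasma volume might increase with body mass index, it does not increase proportionally". If recovery is expressed on one scale for both doses, the smaller IBW dose is expected to give a lower value, and a significant reduction can occur while IBW dosing is comfortably above 66%. If recovery is instead expressed per unit given per actual kilogram, no difference need appear, and a non-significant result does not show that 66% is reached. Someone who sets the planned p-value against the stated null could therefore conclude wrongly in either direction. Someone who takes the 80% as power for the stated hypothesis would misjudge what the trial can show.

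**Working it through.** **1. The two nulls side by side**

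| | Background | Statistics |
|---|---|---|
| Quantity | Recovery with IBW dosing | Recovery with IBW minus recovery with ABW |
| Null | 66% of predicted not reached | Mean difference is zero |
| Role of ABW dosing | None | Comparator |
| Power given | None | 80%, 1 SD, n=16 |

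**2. The protocol's own power figure**

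Inputs from Statistics: difference 1 SD, ICC 0.2, n=16. Assumed: two-sided 5%.

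- SD of the paired difference = √(2 × (1 − 0.2)) = 1.265 SD.
- Standardised effect = 1/1.265 = 0.791.
- Noncentrality = 0.791 × √16 = 3.16 on 15 degrees of freedom; critical t = 2.131.
- Power = 84.0%. By the same method 15 subjects give 81.2%.

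The stated 80% is therefore sound and slightly conservative for the paired test. No term in the calculation involves 66%.

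**3. Does the paired result track the stated null?**

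The protocol gives no mean or SD. Assumed: SD 20 points, mean IBW recovery 1 SD (20 points) below ABW, ICC 0.2, n=16. To test the stated null on the mean, use a one-sample t-test against 66% at one-sided 2.5%, with noncentrality (mean − 66)/20 × √16.

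| True mean, ABW / IBW | Power of paired test | Chance of showing mean IBW recovery above 66% |
|---|---|---|
| 80 / 60 | 84% | 0.1% |
| 90 / 70 | 84% | 11% |
| 100 / 80 | 84% | 74% |
| 110 / 90 | 84% | 99% |

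The paired test behaves identically in all four rows, while the stated null is true in the first row and false in the other three.

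**4. What the planned numbers give for the 66% question**

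Power of the one-sample test (one-sided 2.5%, assumed SD 20):

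| n | True mean 75% | True mean 80% | True mean 90% |
|---|---|---|---|
| 8 (stated minimum) | 20% | 40% | 83% |
| 16 (power statement) | 39% | 74% | 99% |
| 20 (stated maximum) | 48% | 84% | 99.9% |

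The SD matters. At n=16 and a true mean of 80%, power is 94% with SD 15, 55% with SD 25 and 42% with SD 30.

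If every participant reaches 66%, the exact two-sided 95% lower limit for the proportion is 0.025^(1/n): 63% for 8/8, 79% for 16/16 and 83% for 20/20.

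**5. Why the weight behind the prediction must be named**

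The protocol introduces its adult formula with "Sites shall use the following equation to calculate IBW in participants 20 years and older". For a 70-inch man (1.778 m) it gives 50 + 2.3 × 10 = 73 kg. Actual weight is 79.0 kg at BMI 25 and 94.8 kg at BMI 30. A rise that is 66% of a prediction from ideal weight is 66 × 79.0/73 = 71% of a prediction from actual weight at BMI 25, and 66 × 94.8/73 = 86% at BMI 30. The same measurement can fall on either side of 66% depending on the weight used.

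**The case against.** The strongest reply is that the protocol already has a primary endpoint for adequacy. The second primary outcome is the likelihood of under-dosing with IBW, it is estimated from the recovery distribution, and 66% is the obvious cut-off. Statistics also plans distributional summaries for each approach. The paired test is attached to the first endpoint only, and nowhere does the protocol say that its p-value decides the 66% hypothesis. On this view, one linking sentence is missing, and a statistical analysis plan might supply it.

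Much of this stands. It narrows the gap, and it rules out the inference that the hypothesis goes unaddressed. It does not close the gap. The protocol itself fixes a hypothesis with a formal null, a test and a power basis, and the last two do not belong to the first. The second endpoint has no null value or decision criterion, and no stated link to the hypothesis. An analysis plan that carried out the named test faithfully would inherit the mismatch.

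Three stronger readings are tempting and should be set aside.

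- **That the sample-size calculation is wrong.** It is not; it reproduces for the paired difference.
- **That the paired test systematically rejects more often when IBW recovery is adequate than when it is not.** With a fixed SD of 20 and an assumed IBW/ABW dose ratio of 0.82, rejection is 83% at a mean IBW recovery of 90% and 50% at 60%. With a constant 25% coefficient of variation it is 64% at both means. The contrast comes from the assumed variance, and the documents give no SD to choose between the two models.
- **That the unstated under-dosing cut-off, interval method and scale are errors in themselves.** Such details may properly sit in an analysis plan. They matter here only because the mismatch cannot be repaired without settling them.

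**Conclusion.** The point holds: carried out as written, the plan never tests the null it states. That conclusion rests on the protocol's wording alone and needs no numerical assumption.

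The illustrations do rest on assumptions: an SD of 20 points, a 1 SD reduction, two-sided 5% for the paired test, one-sided 2.5% against 66%, and reading the 66% criterion as applying to the mean. On these, paired power stays at 84% while the chance of rejecting the stated null runs from 0.1% to 99%.

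This should be fixed, but it is not fatal. The second primary endpoint already points the right way, and the data needed will be collected anyway.

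**What to change.** 1. In Statistics, define under-dosing for the second primary endpoint as IBW recovery below the protocol's own 66% of predicted. State one weight from which the prediction is computed, the same for both doses.
2. Name as the analysis of the Background hypothesis the mean IBW recovery with its two-sided 95% CI, with the null rejected if the lower limit exceeds 66%. Report the estimated proportion below 66%, with a CI, alongside it.
3. Keep the paired difference with its CI as the comparative estimate. State that the 80% power applies to it alone and that its p-value does not decide whether IBW dosing is adequate.

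Rewording the hypothesis to match the paired test would also remove the inconsistency, but it would abandon the adequacy question that the trial sets out to answer.

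The cost is a few sentences in Background and Statistics, with no new visits or samples. The downside is that limited precision becomes visible. The sponsor must accept the power against 66% shown above (39% to 74% at n=16 for true means of 75% to 80%, and 20% to 40% at the minimum of 8, with SD 20 assumed) or revisit the sample size.

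### For extended half-life products the second PK dose may be given at 72 h, before the last first-dose draw at 93–99 h

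*Protocol*

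**What the plan says.** Three parts of the Protocol bear on this.

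- **Interval to the second dose** (Study design – Primary outcome). For extended half-life products: "at least 72 hours for extended half-life products but no more than 60 days, participant will receive a second dose of factor". The point from which the period runs is not stated. Earlier in the same paragraph, the washout before the first dose uses the same figure and does name its start: "at least 72 hours for extended half-life products since the last dose of factor". The sentence just before the interval says participants "will have pharmacokinetic (PK) labs drawn as described in the PK protocol section".
- **Draw schedule** (PK Protocol). After baseline, extended half-life users are sampled at 30 ± 10 minutes, 5 to 7 h and 20 to 26 h, then at "44 to 50 hours – 69 to 75 hours – 93 to 99 hours". The series is run after each of the two doses. A baseline is also required for each dose: "The baseline and the recovery draws for the first and second doses must be completed by the same laboratory".
- **Outcome served by the late draws** (Secondary outcomes, first entry): "To determine the effect on half-life of these dosing strategies".

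The rules for delaying or repeating a PK episode cover acute bleeds and a missed 30-minute draw. Neither rule ties the second dose to completion of the first sampling series.

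**The concern.** The Protocol gives sites a numerical minimum that is shorter than its own sampling schedule. A site that schedules by the stated 72 h meets the interval rule and still spoils a scheduled sample, because factor from the second infusion is then in the circulation at the first dose's 93–99 h draw. An analysis plan cannot recover that sample.

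At stake is the half-life estimate for the first dose in extended half-life users. A participant dosed at the minimum has five usable post-dose points in period 1 and six in period 2. The loss always falls on period 1, so randomization of sequence should spread it evenly over ideal- and actual-weight dosing. The expected harm is lost precision and an avoidable missing draw, not bias in one direction.

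**Working it through.** **1. Timing, from the Protocol alone**

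- Gap between the earliest second dose and the last first-dose draw: 93 − 72 = 21 h to 99 − 72 = 27 h.
- With the second dose at 72 h, its own 20–26 h draw falls 72 + 20 = 92 h to 72 + 26 = 98 h after the first dose. That coincides almost exactly with the first dose's 93–99 h draw, so one sample would stand for both curves.
- The 69–75 h point is not lost. A second dose at 72–75 h needs its own baseline, which falls in that window; a later second dose leaves the draw undisturbed.
- Standard products are not materially affected. A second-dose baseline at 48–50 h lies within the 44–50 h window, which is the last draw.

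**2. Precision lost with the 96 h point**

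The Protocol gives no peak, half-life or assay error. Assumed: peak 100 IU/dL, half-life 14–20 h, proportional assay error 10%, with or without an additive error SD *s* of 0.5–1 IU/dL. Draw times are set at 0.5, 6, 23, 47, 72 and 96 h. The model is a log-linear fit weighted by the inverse of Var(log level) = 0.10² + (*s*/level)², with level = 100 × 0.5^(t/half-life).

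Proportional error only (*s* = 0):

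- Sum of squares of time: 7210.9 with six points (mean 40.75 h), 3547.8 with five (mean 29.7 h).
- Slope SE = 0.10/√Sxx: 0.00118 with six points, 0.00168 with five. Ratio √(7210.9/3547.8) = 1.43. Moving the last three draws to their window edges gives 1.35–1.51.
- Half-life SE = half-life² × slope SE / ln 2. At 18 h: 324 × 0.00118/0.693 = 0.55 h, rising to 324 × 0.00168/0.693 = 0.78 h.

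With additive error the last point carries less weight, so losing it costs less:

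| Half-life | *s* = 0.5: SE, six → five points | Ratio | *s* = 1: SE, six → five points | Ratio |
|---|---|---|---|---|
| 14 h | 0.64 → 0.66 h | 1.04 | 0.84 → 0.86 h | 1.02 |
| 18 h | 0.77 → 0.89 h | 1.16 | 1.00 → 1.08 h | 1.08 |
| 20 h | 0.86 → 1.05 h | 1.22 | 1.09 → 1.23 h | 1.13 |

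**3. Effect on the participant's paired half-life difference**

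One curve has five points and the other six, so the ratio is √[(SE₅² + SE₆²)/(2 × SE₆²)].

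- Assay error only: 1.23 for *s* = 0, and 1.01–1.12 for *s* = 0.5–1.
- If half-life itself varies between occasions with a CV of 5–10%, 2 × (CV × half-life)² is added to numerator and denominator. The ratio is then 1.003–1.08. The largest value is at 20 h, *s* = 0, CV 5%: √[(0.97² + 0.68² + 2)/(2 × 0.68² + 2)] = 1.08.

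**4. Why the 96 h sample cannot be kept**

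Take an 18 h half-life and a second dose at 72 h that adds 65–100 IU/dL (assumed).

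- True first-dose level at 96 h: 100 × 0.5^(96/18) = 2.5 IU/dL.
- Measured level: 2.5 + 65 × 0.5^(24/18) = 28.3, or 2.5 + 100 × 0.5^(24/18) = 42.2 IU/dL.
- An unweighted six-point log-linear fit that retains this value returns a half-life of 34.9 or 41.3 h in place of 18 h.

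**The case against.** The best defence is that the Protocol, read as a whole, already implies the right order. The full draw schedule is listed with no draw marked optional, the second dose is described after the labs, and "PK studies will be measured in response to one 50 U/kg" does not fit a sample that reflects two infusions. The 72 h figure is a floor with a 60-day ceiling, so both rules can be met by waiting. If the period is counted from the end of the labs, nothing is lost.

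This shows that the rules are compatible and that a careful site would wait. It does not remove the problem. The same paragraph counts the same washout from the last dose, which makes 72 h after the first dose the natural reading, and only the other reading protects the sample.

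The objections on size largely stand:

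- The 1.43-fold figure needs purely proportional error down to levels of about 1–4 IU/dL and no endogenous factor VIII, whereas any severity may enrol. With an assumed endogenous level of 5 IU/dL and proportional error on the total, the ratio falls to 1.06 (14 h), 1.16 (18 h) or 1.20 (20 h).
- The fitted half-life of 35–41 h arises only if an analyst keeps a sample that plainly should be dropped. It shows why the sample is unusable and is not a predicted result.
- A routine prophylactic infusion between 72 and 99 h would spoil the same draw, and a rule about the second study dose alone does not prevent that.

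**Conclusion.** The concern holds, as a minor one. The 72 h minimum is set 21–27 h too short for the Protocol's own extended half-life schedule, and nothing requires the first series to finish before the second dose. This rests on counting the interval from the first dose, which is the natural but not the only reading.

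For a participant dosed before the last draw, the period-1 half-life loses one of six post-dose points. Under the assumptions above, this is a modest loss of precision, and a small one for the paired difference once between-occasion variation is allowed for. It reaches only extended half-life users, whose number is not given, at sites that dose early, whose frequency is unknown. The primary outcomes, sample size and power are not affected.

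**What to change.** In the interval sentence of the study design section, add for extended half-life products only: *the second dose is given only after the last scheduled PK draw of the first dose (93 to 99 hours), and no more than 60 days after the first dose.* This also settles where the interval starts for these products. Standard half-life products need no change.

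The cost is one phrase. The earliest second dose for extended half-life users moves from 72 h to 93–99 h, a delay of 21–27 h. If the sponsor also wants to guard against routine prophylaxis spoiling the late draws, that needs a separate instruction; this wording does not cover it.

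### A bleed that starts after the recovery draw removes an already valid recovery value from the primary analysis

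*Protocol*

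**What the plan says.** The Protocol's section Study design - Primary outcome states: "If the participant has an acute bleed after the recovery draw, then that episode will not be used in the analysis". It continues: "The episode will be attempted again at a later date within the 2-month window". The second sentence shows that the episode meant is the dose with its PK sampling, not the bleed.

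Under Statistics, the first primary endpoint is the mean paired difference in recovery between ideal body weight (IBW) and actual body weight (ABW) dosing. The second is assessed by "extension of estimated recovery distribution to estimate the likelihood of failure (under-dosing or over-dosing) of each dosing strategy". Recovery is the peak level, drawn at 30 ± 10 minutes and set against baseline.

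The PK Protocol section describes the purpose of the other draws: "Blood draws to measure half-life are encouraged to be drawn in the baseline laboratory". Half-life is listed among the secondary outcomes: "To determine the effect on half-life of these dosing strategies". Sampling ends at 44-50 hours for regular half-life products. For extended half-life products the last two draws are at "69 to 75 hours – 93 to 99 hours".

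A missed recovery sample has its own provision: "If the 30-minute recovery draw is missed participant can still be included with another attempt of the dose/PK draw".

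**The concern.** The rule is triggered by an event that comes after the primary measurement is complete. A bleed that begins after the 30-minute draw, and any treatment for it, can affect only samples from 5 hours onward. Nothing in the Protocol limits the exclusion to half-life or keeps the recovery value, so a valid primary value is replaced by a repeat, or the pair is lost if no repeat fits the window. For an extended half-life product, a bleed on day 4 could void a value obtained in the first hour.

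Two things are at stake. One is pairs, in a study powered on 16. The other is selection on an event that may be related to the outcome. If low recovery makes a bleed likelier, low recoveries are preferentially discarded and re-drawn. If IBW dosing gives lower recovery, this happens more often under IBW, which would understate the likelihood of under-dosing with IBW. The trial's hypothesis, recovery of at least 66% of predicted under IBW dosing, depends on that lower tail.

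**Working it through.** **The Protocol's power figure.** Inputs from Statistics: 16 subjects, a 1 SD difference, intra-class correlation (ICC) 0.2. Significance level and sidedness are not stated; two-sided 5% is assumed.

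- SD of the paired difference = √(2 × (1 − 0.2)) = 1.265 SD.
- Noncentrality = √16 / 1.265 = 3.16, with 15 degrees of freedom.
- Paired t-test power is 84.0%, so the stated 80% is met. It is 81.2% with 15 pairs and 78.1% with 14.

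**No link between bleeding and recovery.** The documents give no bleed rate; 5% and 10% per infusion are assumed, with one repeat allowed.

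- Pairs with a valid recovery discarded: 1 − 0.95² = 9.75%, or 1.56 of 16; 1 − 0.90² = 19.0%, or 3.04 of 16.
- Pairs lost because the repeat also bleeds: 1 − (1 − 0.05²)² = 0.5%, or 0.08 of 16; 1 − (1 − 0.10²)² = 2.0%, or 0.32 of 16.
- Bias: none.

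**With a link (illustration).** Simulation of 4,000,000 pairs per setting, in SD units: ABW recovery ~ N(0, 1), IBW recovery ~ N(−1, 1), with a shared person effect giving ICC 0.2. The log-odds of a bleed are logit(p0) − ln(2) × recovery, so the odds double per SD lower recovery; p0 is the bleed risk at the mean ABW recovery. A bled infusion is re-drawn once for the same person, and the pair is dropped if the repeat also bleeds. Repeats that miss the window are not modelled.

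| p0 | ABW infusions with bleed | IBW infusions with bleed | Pairs with a discard | Pairs lost | Mean IBW − ABW (true −1) |
|---|---|---|---|---|---|
| 2% | 2.5% | 4.8% | 7.2% (1.15 of 16) | 0.32% (0.05 of 16) | −0.987 |
| 5% | 6.1% | 11.2% | 16.5% (2.64 of 16) | 1.74% (0.28 of 16) | −0.973 |

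The Protocol gives no SD or expected mean recovery, so the 66% criterion cannot be placed on this scale. The share of IBW recoveries below four possible cuts is shown instead:

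| Cut below the IBW mean | True share | p0 = 2% | p0 = 5% |
|---|---|---|---|
| 0.5 SD | 30.9% | 29.8% | 28.4% |
| 1 SD | 15.9% | 15.0% | 13.9% |
| 1.5 SD | 6.7% | 6.1% | 5.5% |
| 2 SD | 2.3% | 2.0% | 1.7% |

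With ICC 0.8 the effect is smaller: the 1 SD share is 15.5% or 14.7%, and the difference −0.997 or −0.994. With an odds ratio of 1 the true values are recovered. Harsher assumptions move more: with p0 10% and odds tripling per SD, 14% of ABW and 29% of IBW infusions bleed, the difference becomes −0.89 SD and 11% of pairs are lost (1.8 of 16).

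**Against sampling error at n = 16.**

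- Mean difference: SE = 1.265 / √16 = 0.32 SD, against a shift of 0.01-0.03 SD.
- Share below a cut k SD under the mean, from a fitted normal: SE ≈ φ(k) × √((1 + k²/2)/n).
- At k = 1: 0.242 × √(1.5/16) = 7.4 percentage points, against a shift of 0.9-2.0.
- At k = 2: 0.054 × √(3/16) = 2.3 points, against a shift of 0.3-0.6.

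**The case against.** The bias depends wholly on an assumed link. The Protocol gives no bleed rate and no relation between the 30-minute level and bleeding, and its Background describes bleeding as trauma-induced as well as spontaneous. ICC 0.2 is the Protocol's stated minimum, so it shows the effect near its largest for a given link. Any assay noise in measured recovery cannot cause a bleed, yet the model lets it. Even so, the shift is well inside sampling error. Power is hardly touched, and Recruitment allows up to 20 participants against the 16 in the power statement. All of this stands, and it limits the point to a minor one.

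The rule also has a coherent purpose. It is pre-specified, applies to both dosing strategies, provides a repeat that is itself a valid recovery, and takes recovery and half-life from one bleed-free infusion. It also guards against a bleed noticed after the draw but begun before it. That last case is real, but the rule does not separate it from a bleed that truly starts later. The exclusion is bounded in practice by the end of sampling, though that still leaves two to four days.

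Finally, the analysis referred to is not labelled primary, and a SAP, which was not available, might define analysis sets by endpoint. The sentence nevertheless stands under the primary-outcome heading, the only tests the Protocol describes are on recovery, and no exception is made. If only half-life was meant, the text still needs to say so.

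**Conclusion.** The concern holds and is minor. Followed as written, the rule discards completed, valid primary measurements for a reason that bears only on a secondary outcome. That conclusion comes from the text and needs no assumed bleed rate.

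The consequence is small. Without a link between bleeding and recovery, the cost is unnecessary repeat infusions and a fraction of a pair. With the assumed link (odds ratio 2 per SD, 2-5% bleed risk at the ABW mean, ICC 0.2), the likelihood of under-dosing with IBW is modestly understated, by 0.9-2.0 percentage points at a cut 1 SD below the mean. The first primary outcome is unlikely to change. The direction is the awkward part: any such selection favours IBW dosing on the very outcome meant to show its risk.

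**What to change.** Replace the exclusion sentence in Study design - Primary outcome with wording to this effect:

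- If an acute bleed begins after the recovery draw, the completed recovery value is kept for both primary outcomes. Samples taken after bleed onset or its treatment are excluded from the half-life analysis only.
- If the infusion is repeated to obtain half-life, the first valid recovery remains primary, and an analysis using the repeat is reported as a sensitivity analysis.
- If bleed onset is recorded as before the recovery draw, that recovery is not used.

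The management of bleeds is unchanged. The cost is a few sentences and a recorded onset time, which brings some judgement in an open-label study. Some participants would contribute recovery and half-life from different infusions, whereas the present rule takes both from one. In return, data already collected are kept and the primary analysis no longer selects on a post-dose event.
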